- Blood will be counted on a gamma counter after dilution to determine radioactivity on the same day as the scan. After radioactive decay overnight, blood will be disposed of as per routine biohazard.

Non-dosimetry subjects: An IV will be placed to allow injection of the PET tracer, MR gadolinium agent, and glucagon (if needed) during the exams. A less than 9 mCi dose of ¹⁸F-DCFPyL radiotracer will be administered by slow IV push outside the scanner, after which, the subject will be required to sit quietly for 60 minutes to allow for adequate biodistribution of the tracer. The subjects will then be placed in the PET/MR scanner and will remain in the scanner for up to 90 minutes. After which, the whole body (defined in this protocol as base-of-skull to mid-thigh) PET and MR images will be obtained to include images post-intravenous gadolinium contrast. Glucagon (0.5mg-1mg, IV) may be administered by IV prior to the MR imaging if excessive bowel movement is seen on initial images. Glucagon is known to diminish bowel motion and improve MR image quality.

Aims 2 & 3. Sensitivity, specificity, and accuracy values of PSMA-based ¹⁸F-DCFPyL PET and MR imaging and assessment of tumor burden (40 subjects with known or suspected gynecological cancer).

This research visit is estimated to take 2-3 hours. For subjects with gynecologic cancer, the subjects will be in the scanner for up to 90 minutes. The remainder of the time will be preparatory for the scanning. An IV will be placed to allow injection of the PET tracer, MR gadolinium agent, and glucagon (if needed) during the exams. Subjects will be asked to fast for 4 to 6 hours prior to the research visit and to stay well hydrated. There will be a 1-hour uptake period after IV administration of less than 9 mCi of ¹⁸F-DCFPyL radiotracer by slow IV push. After which, the whole body (defined in this protocol as base-of-skull to mid-thigh) PET and MR images will be obtained to include images post-intravenous gadolinium contrast. Glucagon (0.5mg-1mg, IV) may

be administered by IV prior to the MR imaging if excessive bowel movement is seen on initial images. Glucagon is known to diminish bowel motion and improve MR image quality.

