Because the MR scanner is comprised of a very strong magnet, the primary risk associated with MRI imaging is the risk of having ferrous metal in the body such as pins, rods, screws, pacemakers, etc.

Risks will be minimized by making subjects feel as comfortable as possible in the PET/MR scanner. They will be repositioned and provided with as much padding as needed. Subjects will be able to communicate with the imaging staff in the event they decide they cannot continue to lie still for the duration of the study, in which case the study procedure will be terminated. Potential subjects who are asked to participate in MR imaging will be screened for contraindications to MRI and gadolinium contrast.

Gadolinium based contrast agents: Gadobenate dimeglumine be administered according to a weight-based algorithm (0.1 mmol/kg), not to exceed 20 mL. The risks of administering a gadolinium-based agent are exceedingly low; common side effects may include headache, nausea, reaction at injection site, and vasodilatation (temporary widening of a blood vessel) that occurred in less than 3% of subjects. Other less-common side effects reported were bad taste in the mouth, skin rash, dizziness, or warm tingling or burning feeling on the skin.

Acute allergic reactions are extremely uncommon, far less common than occur with iodine-based contrast agents used in CT scanning. To treat unexpected contrast reactions, we maintain a fully up-to-date contrast reaction/resuscitation kit adjacent to our scanners in the UWHC Department of Radiology. The contrast reaction kit is identical to those used throughout our department to treat allergic reactions to iodinated contrast or gadolinium based contrast agents, and is fully stocked with all necessary medications to treat contrast reactions. Further, there is always an experienced radiologist who is trained in treating contrast reactions available within the UWHC during working hours, for this purpose.

There are no immediate benefits anticipated for the participants. This research has a long-term benefit of validating the feasibility of a PET/MR imaging technique with enhanced diagnostic, prognostic and treatment response monitoring capabilities. Ultimately, this trial may allow us to perform PET scans in a much shorter period of time and achieve better quantification.

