All other AEs will be treated as “non serious” and are described in the final study report. An SAE that is definitely, probably or possibly related to the investigational imaging tracer will be reported immediately (within 24 hours of its determination) by telephone or fax by the Principal Investigator.

AE Characteristics: Toxicity will be graded according to the NCI Common Toxicity Criteria (CTCAE), version 4.03 (Appendix A; which can also be accessed and downloaded via the website: <http://ctep.cancer.gov/reporting/ctc.html>). The Investigators will monitor the occurrence of adverse events during the course of each patient in the study. The Investigators need to assess whether there is a reasonable possibility that the study imaging agent caused or contributed to an AE using the following criteria as a guide:

- **Definite:** The adverse event is clearly related to the investigational agent.
- **Probable:** There is a clinically plausible time sequence between the onset of the AE and administration of imaging tracer. The AE is unlikely to be caused by the concurrent/underlying illness, other drugs, or procedures.
- **Possible:** There is a clinically plausible time sequence between the onset of the AE and administration of imaging tracer, but the AE could also be attributed to the concurrent/underlying disease, other drugs, or procedures. “Possibly” should be used when the administration of the study imaging tracer is one of several biologically plausible causes of the AE.
- **Unlikely:** The adverse event is doubtfully related to the investigational imaging tracer.
- **Not Related:** Another cause of the AE is the most plausible and/or a clinically plausible temporal sequence is inconsistent with the onset of the AE and the investigational imaging tracer; and/or a causal relationship is considered biologically implausible.

If any adverse event is considered to be definitely, possibly or probably related to the investigational imaging tracer, that event will be followed until resolution or until it is deemed chronic or irreversible by the Investigator. If an event is unlikely or not related to the investigational imaging tracer, the event will not be reported.

All AE will be documented and recorded in the medical record and will include:

- I. Specific reaction according to NCI Common Toxicity Criteria, version 4.0.
- II. Duration of the reaction

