- III. Severity/grade according to NCI Common Toxicity Criteria, version 4.03. If the adverse event is not addressed by the Common Toxicity Criteria, the severity should be rated as mild (grade 1), moderate (grade 2), severe (grade 3), or life threatening (grade 4).
- IV. Relation of reaction to study agent

V. Management of reaction, including any interruption or dose modification of the study drugs.

Event Severity: In addition to classifying an adverse event as serious or non-serious, the Investigator and/or designated personnel will grade the adverse event to describe the Maximum intensity of the event. Specific criteria for the intensity of adverse events are described in the Common Toxicity Criteria (CTC: National Cancer Institute). Investigators should follow these criteria for grading and reporting adverse events.

An event may be severe, but may not be serious (e.g., severe headache). The severity of an adverse event will be assessed by study personnel using their best clinical judgment and includes but is not limited to taking into account the patient's past history, the patient's chart, interviews with the patient and caregivers, and direct observation. The Investigator will also be asked to assess the possible relationship between the adverse event and the administration of the investigational imaging tracer.

Adverse Event Reporting: Per 21CFR312.32(c), all adverse events deemed both serious and unexpected associated with the use of the drug must be reported to the FDA and to all participating investigators as soon as possible and in no event later than 15 days.

The FDA will be notified of any unexpected fatal or life threatening experience associated with the drug as soon as possible but in no event later than 7 calendar days. The UW HS-IRB will be notified in accordance with posted institutional policy.

Adverse Events: Serious and Non Serious Adverse events will be recorded, regardless of whether or not they are thought to be related to the investigational imaging tracer. While all adverse events will be tabulated and reported in the study final report, serious adverse events will be reported in the course of the trial. Adverse events that meet criteria of a serious adverse event listed above will also be recorded and reported.

The Investigator will inform the IRB of all adverse events attributed to the investigational imaging tracer in accordance with posted institutional policy.

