8.0 PRIVACY AND CONFIDENTIALITY PROTECTIONS

Research procedures will be conducted in private areas and we are only collecting the minimum amount of information necessary to conduct the study. No sensitive data (HIV status, illicit drug use) will be collected. Identifiable records will only be available to study team members.

Data are not being shared outside of UW except through publications, in which case the data do not identify individual subjects. Study data will be managed by Drs. [name] and [name]. Data will not be placed on unencrypted laptop computers. Coded electronic data will be kept on the Obstetrics and Gynecology and Radiology Department secure network drives. A separate file linking codes to subject identity will be kept in the same manner, in a folder separate from study data. At the end of 7 years study data will be de-identified by destroying the link to identifiable

information. Until that time data will remain coded and the file linking codes to subject identity kept as well.

All imaging will be performed for research purposes only and will be given a unique study number that cannot be linked to the patients' medical records in any way. Imaging research images will be stored on PACS under this study number only. The investigators will have access to the patients' electronic medical records that are relevant to this study. Study records will be kept for seven years. Study data will be managed by the PI and co-PI.

Subject's identifiable information will be linked to a study code. The study code will be used to identify the subject and research images. Research images may be used in scientific presentations, but all images will be de-identified. The data will be stored on the Principal Investigator's (PI or co-PI) password protected computer in her locked office. The code will be stored separate from the data on the PI's computer in her locked office.

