(physicians, scientists, imaging modality managers, regulatory and administrative support) and ad hoc members recruited when their expertise is required for the review/monitoring of a research project. MIRS administrative team in addition to a 4-person committee of physicians/scientists will meet annually with representatives from the research team, to discuss research progress, AE/SAE reports, as well as other data reports compiled by the study team. If an AE/SAE occurs, an ad hoc committee meeting will be organized to discuss whether the event is considered serious, whether it can be attributed to research procedures, whether it constitutes non-compliance on the part of the study team, and the plan for resolution and a future remediation plan.

As part of this plan, the monitor(s) will verify that:

- The rights and well-being of human subjects are protected
- Reported study data are accurate, complete, and verifiable from source documents
- The conduct of the study is in compliance with the currently approved protocol, GCPs, applicable regulatory requirements, and guidelines for clinical research studies at the University of Wisconsin-Madison and its affiliates

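### The investigator's causality rating, and the follow-to-resolution and 24-hour SAE duties that depend on it, cover only the tracer, so a reaction best explained by gadobenate or a study blood draw triggers neither duty

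*Combined protocol and SAP*

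**What the plan says.** Section 7.0 (AE Characteristics) defines the causality task with one object: "The Investigators need to assess whether there is a reasonable possibility that the study imaging agent caused or contributed to an AE". The five levels run from Definite to Not Related, and the list of items to record for each event has a single relationship entry, to the study agent.

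Two duties in that subsection depend on the rating:
- Follow-up: "If any adverse event is considered to be definitely, possibly or probably related to the investigational imaging tracer, that event will be followed until resolution". A judgement that the event is chronic or irreversible also ends follow-up.
- Expedited reporting: an SAE rated definitely, probably or possibly related to the tracer is reported within 24 hours.

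Not Related applies, among other cases, when "Another cause of the AE is the most plausible".

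The tracer is not the only research exposure. Section 5.0, for all non-dosimetry imaging, says: "An IV will be placed to allow injection of the PET tracer, MR gadolinium agent, and glucagon (if needed) during the exams". Section 8.0 says: "All imaging will be performed for research purposes only". For gadolinium, section 6.0 says "common side effects may include headache, nausea, reaction at injection site, and vasodilatation", at a rate below 3%, and it separately lists nausea, lightheadedness and fainting for blood collection. For glucagon it gives contraindications and tolerability but no list of reactions.

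Section 9.0 uses a wider attribution: when an AE or SAE occurs, an ad hoc committee considers, among other things, "whether it can be attributed to research procedures".

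**The concern.** Women in this trial receive gadobenate, and some have blood drawn, only because they are in the trial. A reaction to either is research harm in the same sense as a reaction to the tracer. The duties that guarantee follow-up to an end point and fast escalation are nevertheless conditional on the tracer being at least a possible cause. The more confidently an investigator assigns a reaction to the contrast agent, the fewer duties apply.

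At stake is assured handling of a contrast or blood-draw reaction that is serious or slow to resolve. The safety record is also less informative, because it has no place to name the exposure thought responsible.

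**Working it through.** **Step 1. Follow one event through the rules.** A non-dosimetry subject receives the tracer, waits 60 minutes, enters the PET/MR scanner and is given gadobenate (section 5.0). Suppose she reacts at the gadobenate injection and the investigator judges contrast the most plausible cause.

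| Rule | Condition | Met? |
|---|---|---|
| Causality level (section 7.0) | Another cause most plausible | Not Related |
| Follow-up to resolution (section 7.0) | Definitely, probably or possibly tracer-related | No |
| 24-hour SAE report (section 7.0) | Same | No |
| Recording and final-report tabulation (section 7.0) | Any AE | Yes, no follow-up duty |
| SAE reporting during the trial (section 7.0) | Any SAE | Yes if serious, no deadline given |
| Ad hoc committee (section 9.0) | Any AE or SAE | Yes, not linked to the two triggers |
| Phone call and return exam (section 5.0) | Call to all at about 1 to 3 days; exam if late effects are present | Yes, not follow-up to resolution |

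Section 5.0 also makes a gadolinium contrast reaction a ground for removal from the study. The protocol therefore foresees this event, yet states no follow-to-resolution duty for it.

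**Step 2. Check the IRB rule.** Section 7.0 says: "The Investigator will inform the IRB of all adverse events attributed to the investigational imaging tracer", subject to posted institutional policy. A second sentence there says the IRB will be notified under that policy, in a paragraph about the drug. The policy is not in the documents, so whether a contrast reaction would escape IRB notice cannot be determined.

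**Step 3. Check for internal conflict.** AE Characteristics says that events unlikely or not related to the tracer will not be reported. Later in section 7.0, all adverse events are to be tabulated and reported in the final report. A contrast reaction graded Not Related falls under both statements.

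**Step 4. Count the exposed women.**
- Gadobenate: 52 enrolled minus up to 6 dosimetry subjects = at least 46.
- Study blood draws: the first 3 dosimetry subjects and, as needed, the other 3, so 3 to 6.

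**Step 5. Scale.** The plan gives no expected event count to reproduce. With n women and rate p per woman, the expected number is n × p and the chance of at least one is 1 − (1 − p)^n. The only rate in the documents is below 3%, so 3% is an upper bound; 1% and 2% are assumptions.

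| n | p | Expected | Chance of at least one |
|---|---|---|---|
| 46 | 1% | 46 × 0.01 = 0.46 | 1 − 0.99^46 = 37% |
| 46 | 2% | 46 × 0.02 = 0.92 | 1 − 0.98^46 = 61% |
| 46 | 3% | 46 × 0.03 = 1.38 | 1 − 0.97^46 = 75% |
| 52 | 3% | 52 × 0.03 = 1.56 | 1 − 0.97^52 = 79% |

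The last row covers the case in which every subject receives contrast.

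**The case against.** The strongest reply is that other provisions already cover these events. The committee in section 9.0 considers attribution to research procedures and a plan for resolution. Section 7.0 records every AE whatever its cause and reports SAEs during the trial. Every subject is phoned, and section 6.0 provides a contrast-reaction kit and a trained radiologist. All of this stands. A reader might infer that causality is assessed against nothing but the tracer anywhere in the protocol, or that research harm is neither followed nor escalated; the documents support neither. What these provisions do not supply is a deadline or a follow-to-resolution duty for a non-tracer reaction.

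A reader might also infer that contrast effects will be charged to the tracer, because Possible applies when the tracer is one of several plausible causes. That goes too far. The definitions tell the investigator to weigh other drugs and procedures, Possible expresses uncertainty, and it triggers both duties, so it errs towards safety. The residual point is only that the record has no field for the other candidate cause.

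Finally, the probabilities in the working do not measure missed 24-hour reports. They concern common side effects, most of which would not be serious, and section 6.0 describes acute allergic reactions as extremely uncommon. No rate is given for serious or unresolved contrast events. This objection stands and limits the weight of the figures.

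**Conclusion.** The concern holds in a limited form and is best classed as a cheap improvement. The investigator's causality scale, the AE relationship entry, the follow-to-resolution rule and the 24-hour SAE rule all refer to the tracer alone, and the committee's wider attribution is not connected to them. In practice the gap concerns gadobenate, in at least 46 of 52 women, and blood draws in 3 to 6. Glucagon is a further research exposure, but section 6.0 lists no reactions to it.

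As an upper bound on mostly mild reactions, about 1.4 events and a 75% chance of at least one are expected at 3%; at an assumed 1%, about 0.5 and 37%. These figures assume that all 46 receive contrast, that the rate applies per woman, and that women react independently. That the IRB would not hear of such events might be inferred, but this cannot be shown without the institutional policy.

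**What to change.** In section 7.0:
- Beside the relationship to the tracer, record the relationship to other research products or procedures: at least gadobenate, glucagon if given, and blood draw.
- Key the follow-to-resolution and 24-hour SAE sentences to any research product or procedure.
- State that a section 9.0 committee attribution to research procedures activates the same two duties.
- Align the IRB sentence with institutional policy.
- Keep tracer-specific attribution for the IND reports.
- Reconcile the statement that events unlikely or not related to the tracer will not be reported with the commitment to report all AEs.

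The cost is a few sentences of protocol text and a few fields on the AE form. The downside is a few more events to follow and report.

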7.0 ADVERSE EVENTS AND SAFETY ISSUES

Definition of adverse events and potential risks: The term “adverse event” is defined in the International Conference on Harmonization Guideline for Good Clinical Practice as follows: “Any untoward medical occurrence in a patient or clinical investigation subject administered a pharmaceutical product and which does not necessarily have a causal relationship with this treatment. An adverse event (AE) can therefore be any unfavorable and unintended sign (including an abnormal laboratory finding), symptom, or disease temporally associated with the use of a medicinal (investigational) product whether or not related to the medicinal (investigational) product”.

Medical conditions of a subject that exist prior to receiving the investigational imaging tracer will be recorded as medical history. After administration of the investigational imaging tracer, all new medical conditions are considered adverse events. Adverse events occurring in this trial will be recorded in data collection forms, regardless of whether or not they are thought to be associated with the investigational imaging tracer throughout the study period. However, the Investigator also will assess the possible relationship between the adverse event and the investigational imaging tracer.

For the purposes of this protocol, an adverse event (AE) is any untoward medical occurrence (e.g., sign, symptom, disease, syndrome, intercurrent illness, abnormal laboratory finding) that emerges or worsens relative to pre-imaging baseline. We anticipate minimal adverse effects or toxicity with the investigational imaging tracer ¹⁸F-DCFPyL in this study.

Definition of Serious Adverse Events (SAE), SAE list: Any adverse drug experience, occurring at any dose that results in any of the following:

- Death
- Is life-threatening (an event in which the patient was at immediate risk of death; it does not refer to an event which hypothetically might have caused death if it were more severe)
- Requires or prolongs inpatient hospitalization
- Results in a persistent or significant disability/incapacity
- Is a congenital anomaly/birth defect
- Important medical events that may not result in death, be life-threatening, or require hospitalization may be considered serious when, based upon appropriate medical judgment, they may jeopardize the patient or subject and/or may require intervention to prevent one of the outcomes listed.

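### Section 7.0 says adverse events judged unlikely or not related to the tracer will not be reported, yet elsewhere puts all adverse events in the final report; the sentence needs a stated scope

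*Combined protocol and SAP*

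**What the plan says.** All the statements below are in Section 7.0 unless noted.

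- **Recording.** AEs are to be entered on the study's forms "regardless of whether or not they are thought to be associated with the investigational imaging tracer". The part on serious and non-serious events repeats this: "Adverse events will be recorded, regardless of whether or not they are thought to be related to the investigational imaging tracer".
- **Non-serious events.** The text after the SAE list says that all other AEs are treated as non-serious "and are described in the final study report". No attribution condition is attached.
- **Attribution.** "The Investigators need to assess whether there is a reasonable possibility that the study imaging agent caused or contributed to an AE". The scale has five categories: Definite, Probable, Possible, Unlikely and Not Related. It concerns the tracer only.
- **The disputed sentence.** After the scale, and directly after a rule on following up related events, comes: "If an event is unlikely or not related to the investigational imaging tracer, the event will not be reported".
- **Final report.** Later in the section: "all adverse events will be tabulated and reported in the study final report". The same sentence has serious events reported while the trial is under way.
- **Prompt reports.** Three other rules are stated separately: a 24-hour report for SAEs at least possibly related to the tracer, the FDA 7- and 15-day rules, and notice to the IRB of events attributed to the tracer.
- **External oversight (Section 9.0).** A committee meets annually over AE/SAE reports and other data compiled by the study team. It also meets ad hoc when an AE or SAE occurs, to consider seriousness and whether research procedures were the cause.

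**The concern.** For an event classed as Unlikely or Not Related, one instruction says not to report it and others say to report it. Staff cannot comply with both, and the text does not say which prevails.

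What is at stake is the completeness of the safety report. If the disputed sentence governed, inclusion would turn on an investigator's judgement about one agent. The study also gives gadolinium and, where needed, glucagon, and it draws blood from dosimetry subjects (Section 5.0); Section 6.0 lists risks of gadolinium and of blood collection. An event for which one of these is judged the most plausible cause meets the definition of Not Related.

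The committee in Section 9.0 is meant to discuss whether research procedures caused an event. It works from what the study team compiles, so a filter applied beforehand could keep from it some of the events it is there to consider.

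**Working it through.** No figure in the plan is in dispute, so the check is a comparison of rules.

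**Step 1. Apply each rule to each kind of event.**

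| Event | Disputed sentence | Other statements in Section 7.0 | Result |
|---|---|---|---|
| Non-serious; Definite, Probable or Possible | no bar | in the final report | consistent |
| Non-serious; Unlikely or Not Related | not reported | in the final report | conflict |
| Serious; Definite, Probable or Possible | no bar | 24-hour report, in-trial reporting, final report | consistent |
| Serious; Unlikely or Not Related | not reported | in-trial reporting, final report | conflict |

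The conflict covers two of five attribution categories, at both levels of seriousness.

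**Step 2. Separate recording from reporting.** The two statements that apply regardless of attribution concern recording. They do not contradict the disputed sentence, because an event can be recorded and left out of a report. The contradiction is with the two final-report statements and the in-trial reporting of serious events.

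**Step 3. Ask whether the sentence has an implied scope.** It names no recipient, document or deadline. It stands with the attribution scale, not in the part headed Adverse Event Reporting. The 24-hour and IRB rules already carry their own attribution conditions, and the FDA rules are limited to events associated with the drug. None of them needs this sentence in order to work. A limit to prompt reporting is therefore possible, but nothing in the text states it.

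**Step 4. Trace events caused by procedures.** Not Related applies, among other grounds, when a different cause is the most plausible one. Possible applies when the timing fits and the tracer is only one candidate, with other drugs or procedures among the alternatives. An event after gadolinium, glucagon or a blood draw can fall in either category. Under the disputed sentence the first kind would be left out and the second kept.

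**Step 5. Trace the route to the committee.** Section 9.0 puts no attribution condition on the ad hoc meeting. Its annual input is AE/SAE reports and data prepared by the study team. If the disputed sentence is applied to those reports, the committee may not see Unlikely or Not Related events. If it is not applied, the committee sees them all. The documents do not settle which.

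**The case against.** The strongest reply is that the sentence is about prompt reporting only. The final report is addressed twice in Section 7.0, inclusively both times, and the disputed sentence does not mention it. The sentence stands beside a follow-up rule for related events, and the next statement requires all AEs to be documented, including their relation to the study agent. The 24-hour and IRB rules use the same kind of filter. This may well be what was intended. What stands is that the wording carries no such limit, and that a serious event classed as Unlikely or Not Related is still covered by the in-trial reporting commitment.

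Other parts of the reply limit how far the point reaches:

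- A reader might infer that safety data will be lost. They will not be lost at collection: every event is recorded, and a full table can be built if the final-report statements are followed.
- A reader might infer that all events from gadolinium, glucagon or blood draws drop out. The Possible category keeps those for which the tracer remains a plausible contributor, and Section 9.0 provides for review of procedural causes.
- A reader might take a size from the phase I summary in Section 11.0. There, 2 of 9 patients had three events, none attributed to the tracer. Reporting all events gives 2/9 = 22.2% (exact 95% interval 2.8% to 60.0%); filtering on attribution gives 0/9. This shows how the rule works, but it is no estimate for this trial. It comes from another study, and one of the two patients counts only through a platelet fall found at routine post-imaging assessment. The follow-up described here is a phone call at about 1 to 3 days.
- A reader might argue that the tracer is new to women and that this raises the stakes. The documents do not establish that.
- Open-label attribution does not bias a comparison here. Every subject is to receive the tracer, there is no untreated arm, and the statistical section contains no safety endpoint or decision rule.

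**Conclusion.** The inconsistency is real and should be resolved. A stated rule, if followed as written, would leave recorded events out of safety reports, and other statements in the same section say the opposite. It is more than missing detail, because the text gives an instruction that staff could act on.

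The reach is Unlikely and Not Related events of any seriousness, in the final safety table and possibly in the committee's material. No number of events or rate can be attached, because the plan states no expected adverse event rate. The consequence depends on the disputed sentence being applied beyond prompt reporting, which the documents neither require nor rule out. They do not support a conclusion that events will be suppressed, only that the plan as written permits it.

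**What to change.** Reconcile the statements in Section 7.0 and align them with Section 9.0:

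1. Limit the disputed sentence to the prompt reports that depend on attribution. For example: *Events judged Unlikely or Not Related do not trigger the 24-hour SAE report or the IRB notice.* The FDA rules keep their own wording, and the commitment to report serious events during the trial remains.
2. Add: *Every recorded adverse event, whatever its attribution, is included in the final-report table and made available to the monitoring committee. Attribution is shown as a column and is not used to select events.*

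The cost is one clause, one added statement and a somewhat longer table. No new data are needed, since relation to the study agent is already recorded for each event. Separate attribution columns for gadolinium, glucagon and other procedures could help the committee, but they are a matter of preference and the reconciliation does not depend on them.
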